9.3.3.2. Analysis of Secondary Endpoints

The key secondary endpoint (change from baseline in caudate volume as assessed via vMRI at Month 12) will be analyzed by a mixed model repeated measures (MMRM) model using all available vMRI data up to the Month 12 Visit. The model will include fixed effects for treatment, baseline vMRI, and disease stage (by PIN_{HD} bin for Stage 2 only and by TFC for Mild Stage 3 only). The intercept and time of collection will be included as a random effect nested within subjects. The unstructured covariance matrix will be used in the model. The rate of changes will be compared between treatments and the least squares (LS) mean differences at Month 12 will also be provided.

For change from baseline in cUHDRS, a MMRM analysis (repeat at visit) will be performed using all data collected up to 12 months. The model will use treatment group, visits (categorical), treatment by-visit interaction, disease stage as fixed factors, CAG, age, and CAG by age interaction as covariates. The LS mean estimates for the change from Month 12, the difference between pairwise comparison with placebo, confidence intervals, and 2-sided p value will be presented. A similar model will be used for UHDRS sub-scores and PBA-s. Rate of changes in these scores will also be explored.

For by disease stage analyses, PIN_{HD} category (0.180 to 0.679, 0.680 to 1.520, or 1.521 to 4.930) will be used as a fixed factor for Stage 2 only, and TFC score (11, 12, or 13) will be used as a fixed factor for Mild Stage 3 only.

A repeated measure analysis model, similar to the analysis model used for blood tHTT protein, will be used for blood and CSF mHTT protein. Dose-response relationships will be explored and a by-visit summary of blood tHTT and blood and CSF mHTT protein will be displayed.

An analysis of covariance model with dose and Baseline in the model will be used to analyze change from Baseline to Month 12 in mHTT protein (in blood and CSF). Nominal p values and 95% confidence interval for each pairwise comparison will be calculated.

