Blood tHTT protein	Completers of Stage 2 and Mild Stage 3 HD subjects aged 25 years and older as defined by the protocol I/E criteria (ITT Population completers)	Change from baseline in blood tHTT protein at Month 3	Discontinuation of study treatment (due to any reason); data after the last dose of study drug + 30 days will be excluded.	Same as primary analysis for primary efficacy endpoint	Sensitivity analysis for primary endpoint
Blood tHTT protein	Stage 2 and Mild Stage 3 HD subjects aged 25 years and older as defined by the protocol I/E criteria (ITT Population)	Change from baseline in blood tHTT protein at Month 3	Discontinuation of study treatment (due to any reason); data after the last dose of study drug + 30 days will be excluded.	Treatment difference and corresponding 95% CI between each PTC518 dose group and placebo group in the change from baseline in blood tHTT protein at Month 3 will be estimated using a MMRM model, with missing data imputed using a control-based method.	Sensitivity analysis for primary endpoint
Caudate volume via vMRI	Stage 2 and Mild Stage 3 HD subjects aged 25 years and older as defined by the protocol I/E criteria (ITT Population)	Percent change from baseline in caudate volume as assessed via vMRI at Month 12	Discontinuation of study treatment (due to any reason); data after the last dose of study drug + 30 days will be excluded.	Treatment difference and corresponding 95% CI between each PTC518 dose group and placebo group in the percent change from baseline in caudate volume at Month 12 will be estimated using a MMRM model.	Analysis of key secondary endpoint
cUHDRS	Stage 2 and Mild Stage 3 HD subjects aged 25 years and older as defined by the protocol I/E criteria (ITT Population)	Change from baseline in cUHDRS scores at Month 12	Discontinuation of study treatment (due to any reason); data after the last dose of study drug + 30 days will be excluded.	Treatment difference and corresponding 95% CI between each PTC518 dose group and placebo group in the change from baseline in cUHDRS scores at Month 12 will be	Analysis of secondary endpoint

Endpoint	Population	Variable	Intercurrent events	Population level summary	Analysis
				estimated using an analysis of covariance (ANCOVA) model.	

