3.4.3. Volumetric Magnetic Resonance Imaging

The loss of brain tissue is a continuous variable of disease progression in HD. Volumetric Magnetic Resonance Imaging (vMRI) will be used to effectively assess potential changes in brain volume (whole brain, lateral ventricles, caudate, and putamen volumes) to help determine if the treatment affects the rate of volume loss.

The vMRI images will be used to detect changes in brain volume in different areas over time using the boundary shift integral (BSI) technique. The BSI technique uses the shift in intensity differences on a pair of registered intensity-normalized images to quantify the difference between the 2 images (i.e., to quantify the amount of change in those selected brain regions). This technique is considered the gold standard to measure global brain or regional atrophy (tissue loss) and the output of BSI method is the change from baseline in volume (atrophy or expansion) over time.

The following regional brain volumes and measurements of volume change over time will be assessed at Visit 2 (Baseline) and Visits 5 (Month 3) and 8 (Month 12) in the six brain regions listed below:

- Whole Brain
- Lateral Ventricle
- Left Caudate
- Right Caudate
- Left Putamen
- Right Putamen

For regions including the whole brain, lateral ventricles, left caudate, and right caudate, the vendor will supply the absolute baseline volume and the change in volume from baseline using baseline as a reference timepoint. To estimate volume at Visits 5 (Month 3) and 8 (Month 12), BSI volume change will be subtracted or added to the baseline volume depending on the region.

For the whole brain and caudate areas, a positive BSI value means a decrease in volume (also known as atrophy), thus, the estimated volume at follow-up will be calculated as follows:

$$\text{Volume}_{\text{Follow-up}} = \text{Volume}_{\text{baseline}} - \text{Volume Change}_{\text{Follow-up}}$$

In addition, volume and volume change for the left and right caudate volume will be reported separately. To estimate total caudate volume, the left and right volume and volume change estimates will be summed.

For the lateral ventricles, a positive BSI value means an increase in volume (also known as expansion), thus, the estimated volume at follow-up will be calculated as follows:

$$\text{Volume}_{\text{Follow-up}} = \text{Volume}_{\text{baseline}} + \text{Volume Change}_{\text{Follow-up}}$$

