3.4.7. Multiplicity Control

For the primary efficacy analysis, to control the family-wise Type I error at the 0.05 level, a fixed sequence (hierarchical) testing procedure will be employed, where the treatment effect between PTC518 10 mg versus placebo will be tested first at the significance level of 0.05 (2-sided) and if p-value < 0.05 , the treatment effect between PTC518 5 mg versus placebo will be tested at the significance level of 0.05 (2-sided).

The secondary and exploratory efficacy endpoints will be analyzed at the significance level of

0.05 (2-sided) without multiplicity adjustment.

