5.3. Secondary Endpoints Analysis

Key Secondary Endpoint Analysis

The percent change from baseline in caudate volume as assessed via vMRI at Month 12 is the key secondary endpoint.

A MMRM model will be used to compare each PTC518 dose group with placebo group for the percent change from baseline in caudate volume as assessed via vMRI at Month 12. The response variable is the percent change from baseline in caudate volume. The model will include fixed effects for treatment, disease stage (by PINHD bin for Stage 2 only and by TFC for Mild Stage 3 only) with baseline caudate volume as a covariate. The time and time by treatment interactions will be included in the model where time is defined as: date of caudate assessment – date of randomization + 1. The intercept and time of collection will be included as a random effect nested within subjects.

The unstructured covariance matrix will be used in the model. If the model does not converge under the unstructured covariance matrix, the Variance Component covariance matrix will be used/. If the model still does not converge, the random effect will be excluded. The treatment effect and treatment difference will be estimated by the LS means and the difference in LS means, along with their SE and with 95% CIs, and the nominal p-values (2-sided) for each pairwise comparison (PTC518 vs. placebo) will be provided.

The caudate volume (left, right, and total [left + right]) and percent change from baseline will be summarized descriptively by treatment group for each visit.

Other Secondary Endpoints Analysis

Other secondary endpoints include:

- Change from baseline in cUHDRS scores at Month 12

An ANCOVA model will be performed to compare each dose group with placebo group for the change from baseline in cUHDRS at Month 12. The model will include treatment group as the independent variable and baseline cUHDRS, disease stage, CAG, age, CAG by age interaction as covariates. The treatment effect and treatment difference will be estimated by the LS means and the difference in LS means, along with their SE and with 95% CIs, and the nominal p-values (2-sided) for each pairwise comparison (PTC518 vs. placebo) will be provided.

- Change from baseline in blood tHTT protein at Month 12

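### The last convergence fallback for the key secondary caudate model pools the Month 3 and Month 12 variances, so the Month 12 standard error is wrong if that step is reached and the variances differ (minor)

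*SAP*

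**What the plan says.** Table 1 in SAP 3.1 sets the key secondary estimand as the treatment difference "in the percent change from baseline in caudate volume at Month 12 will be estimated using a MMRM model". SAP 3.4.3 schedules scans at baseline, Month 3 and Month 12, so each subject has two planned post-baseline values.

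The model in SAP 5.3 has treatment, disease stage stratum, baseline caudate volume, continuous time and time by treatment. For within-subject dependence it says: "The intercept and time of collection will be included as a random effect nested within subjects". An unstructured matrix is tried first. If that fails, "the Variance Component covariance matrix will be used". The last step is "If the model still does not converge, the random effect will be excluded". No residual structure, visit-specific variance or robust standard error is given for that step. The LS mean differences, SEs, 95% CIs and nominal p-values come from whichever model converges.

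Protocol 9.3.3.2 gives no fallback. It asks for the Month 12 LS mean differences and adds: "The rate of changes will be compared between treatments".

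**The concern.** The random intercept and random time carry all the within-subject covariance and are the only way the model lets variance differ between visits. Without them the model is ordinary least squares with a single residual variance. Scans fall near two time points and time by treatment is in the model, so the Month 12 contrast rests almost entirely on Month 12 data. Its standard error is nevertheless computed from a variance averaged over both visits.

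At stake are the confidence interval and nominal p-value of the only endpoint labelled key secondary. SAP 3.2 calls for analysis overall and separately by disease stage, so the fallback chain may be run three times, twice on roughly half the data.

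**Working it through.** **Inputs.** From the documents: two post-baseline scans, the fallback order, and about 144 subjects in Parts A, B, D and E randomised 2:1. With placebo pooled that gives three arms of 48. The documents state no SD, SE or power for caudate volume, so there is no plan figure to reproduce. Assumed: r = Var(Month 3)/Var(Month 12), taken on both sides of 1, and m, the fraction of Month 12 scans missing.

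**Which covariance is left.** If the covariance names describe the random effects, excluding them leaves one residual variance. If they describe the residual matrix, it has already become Variance Component, again one variance. Both readings end in the same place.

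**Formula.** The true variance of the Month 12 contrast is proportional to Var(Month 12). The model uses the pooled value. So

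- reported SE / true SE = sqrt((r + 1 − m)/(2 − m)), which is sqrt((1 + r)/2) when m = 0
- two-sided type I error = 2 × (1 − Φ(1.96 × ratio))

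Example with r = 0.2, m = 0: sqrt(1.2/2) = 0.77, and 1.96 × 0.775 = 1.52, giving 12.9%. With r = 0.2, m = 0.2: sqrt(1.0/1.8) = 0.745, giving 14.4%.

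| r | SE ratio, m = 0 | Type I error, m = 0 | Type I error, m = 0.2 |
|---|---|---|---|
| 0.2 | 0.77 | 12.9% | 14.4% |
| 0.5 | 0.87 | 9.0% | 9.6% |
| 1.0 | 1.00 | 5.0% | 5.0% |
| 1.56 | 1.13 | 2.7% | 2.5% |
| 2.0 | 1.22 | 1.6% | 1.5% |

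**Limit as r goes to 0.** The ratio becomes sqrt((1 − m)/(2 − m)). With m = 0 it is 0.707 (16.6%). With m = 0.15 it is sqrt(0.85/1.85) = 0.678 (18.4%). With m = 0.20 it is sqrt(0.8/1.8) = 0.667 (19.1%).

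**What a random slope would imply.** Suppose SD² = slope variance × t² + measurement-error variance, with t in years (0.25 and 1). If the slope SD equals the error SD, r = 1.0625/2 = 0.53, the ratio is 0.875 and the error 8.6%. If measurement error is twice the slope SD, r = 4.0625/5 = 0.81, the ratio is 0.952 and the error 6.2%. These are illustrations, not estimates.

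**Simulation under the null** (3 arms of 48, six strata, a baseline covariate, within-subject correlation 0.4; results for r = 0.2, 0.5, 1.0, 1.56):

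- No missing scans, 10,000 trials per r: last step 12.6, 9.5, 5.1, 2.5%. A Month 12 ANCOVA gave 4.6 to 5.5%.
- 15% of Month 12 scans missing, 2,000 trials per r (Monte Carlo SE about 0.5 points): last step 14.9, 9.8, 4.2, 3.1%. An unstructured 2x2 visit model gave 4.9, 5.8, 4.3, 5.3%, with no non-convergent or singular fit in 8,000 trials. A Month 12 ANCOVA gave 5.5, 6.0, 4.4, 5.3%.

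A separate simulation with jittered scan dates gave SE ratios that agreed with the closed form at within-subject correlations of 0, 0.5 and 0.8.

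**The case against.** The strongest objection is that the step will hardly ever be used. It needs two successive failures. The Variance Component step has three covariance parameters and lets variance grow with time, so it suits the very case in which the last step would do harm. It converged in all of 1,280 simulated trials in one check and all of 2,400 in another. In the second check its own type I error was 5.3 to 7.0% at r = 0.2 and 0.5. The endpoint is also outside the multiplicity scheme: SAP 3.4.7 says "The secondary and exploratory efficacy endpoints will be analyzed at the significance level of" 0.05 without adjustment.

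This stands as a limit on severity. It does not remove the defect. The first step is fragile, with four covariance parameters for three estimable moments at two nearly fixed times. Convergence also depends on software and time scale: the SAP defines time in days, and a small check with time in days, a general optimiser and 50 iterations did produce Variance Component failures (8 trials per setting, so indicative only). The simulated convergence rates come from purpose-written code, not SAS.

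A second objection is that the SAP calls the model an MMRM and does not exclude a residual structure once the random effect is gone. That is fair, but none is named.

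The contrast with the primary endpoint helps only in part. Its fallback list in SAP 5.1 keeps within-subject correlation to the end, but its last three entries also assume equal variances.

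Three stronger readings are tempting. A reader might infer that the caudate test runs at 9 to 15% type I error. Those figures apply only if the last step is reached and Month 12 is clearly more variable. A reader might infer that the standard error must be too small. The random time term is consistent with growing variance, but the documents give no SDs, and with r above 1 the error goes the other way. In the reassuring direction, a reader might take 3/1,280 = 0.23% as an upper bound on reaching the step and conclude that the overall error rises by at most 0.0023 × (16.6 − 5.0) = 0.03 points. That bound is specific to one program and to assumed SDs.

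**Conclusion.** The point holds as a minor, conditional one. As written, the last fallback gives the Month 12 difference a standard error based on a variance pooled over Months 3 and 12. If it is reached, two-sided type I error is about 12.9% at r = 0.2 and 1.6% at r = 2.0 without missing scans, is nominal at r = 1, and cannot exceed 16.6% (18.4% with 15% and 19.1% with 20% of Month 12 scans missing). These figures assume that nearly all scans fall near the two visits, that residuals are independent at the last step, and that model-based standard errors are used. The direction depends on r, which the documents do not give. The step is probably rare, and no firm unconditional error rate should be claimed.

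**What to change.** Keep the unstructured and Variance Component steps. Replace only the last sentence, before unblinding, with wording such as:

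> If the model still does not converge, a categorical-visit MMRM for Months 3 and 12 will be fitted, with treatment, visit, treatment by visit, disease stage stratum and baseline caudate volume, and an unstructured 2x2 within-subject covariance matrix. If that does not converge, the Month 12 value will be analysed by ANCOVA with treatment, disease stage stratum and baseline caudate volume.

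The final step has a precedent in the same section, which for cUHDRS says: "An ANCOVA model will be performed to compare each dose group with placebo group for the change from baseline in cUHDRS at Month 12".

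The cost is one SAP sentence, with no change to data collection. There are three downsides, all arising only if both random-effects steps fail:

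- This model gives no random-slope comparison of rates, so the rate comparison in Protocol 9.3.3.2 would not come from it.
- Scans on days 121 to 330 fall in neither the Month 3 window (76 to 120) nor the Month 12 window (331 onward) of SAP Table 2. Some early-termination scans would therefore not be used, although the present last step would use them.
- The ANCOVA omits subjects without a Month 12 scan.

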Clinical laboratory assessments	X	X		X	X	X	X	X	X					Safety laboratory assessments at Baseline should be performed fasted. All other safety laboratory assessments are not required to be performed fasted. Serology performed at Screening only.
CSF collection		X				X	X	X	X					It is recommended that CSF collection be done at least 3 days prior to Day 1. Sample collection may be done up to 8 days prior to Visits 5 through 8. CSF collection must be performed predose.
UHDRS Part I (Motor Assessment)	X		X			X	X	X	X					
UHDRS Part II (Cognitive Assessment)	X (SDMT only)		X	X (SDMT only)	X (SDMT only)	X (SDMT only)	X (SDMT only)	X (SDMT only)	X					At Screening, only SDMT is required to confirm eligibility. Only SDMT is done at Visits 3, 4, 5, 6, and 7.
UHDRS Part IV (Functional Assessment)	X		X			X	X	X	X					

	Screening	Baseline		Treatment Period						Safety Follow-Up			Notes	
		Days -57 to -8	Days -22 to -1	Day 1	Month 1	Month 2	Month 3	Month 6	Month 9	Month 12 /EOS/ EOT /ET	Month 13	Month 16	Month 18	
Study Month														The Safety Follow-up visits must be performed for all subjects following either the EOT or ET visit.
Visit	1	2		3	4	5	6	7	8	9	10	11		
Window (days)				±7	±7	±7	±7	±7	±7	±7	±7	±7		
UHDRS Part V (Independence Scale)	X		X			X	X	X	X					
UHDRS Part VI (Functional Capacity)	X		X			X	X	X	X					
UHDRS Part VII (Clinical Summary)			X			X	X	X	X					
UHDRS Part VIII (Clinical Disposition)			X			X	X	X	X					
PIN _{HD} Calculation	X													TMS and SDMT will be performed at this visit to calculate PIN _{HD} . Only subjects who qualify for enrollment into the Stage 2 group will have PIN _{HD} calculated.
PBA-s			X						X					The PBA-s will be used instead of Part III of the UHDRS.
Timed Up and Go (TUG), 2-minute walk test, and postural sway test			X			X	X	X	X					The Opal wearable device will be worn during these assessments. Each test will be conducted twice: once with a concurrent cognitive interference task and once without.
FuRST 2.0			X			X	X	X	X					
vMRI			X			X			X					Imaging can be done up to 8 days prior to all vMRI visits after Screening.

	Screening	Baseline		Treatment Period						Safety Follow-Up			Notes
		Days -57 to -8	Days -22 to -1	Month 1	Month 2	Month 3	Month 6	Month 9	Month 12 /EOS/ EOT /ET	Month 13	Month 16	Month 18	
Study Month													The Safety Follow-up visits must be performed for all subjects following either the EOT or ET visit.
Visit	1	2		3	4	5	6	7	8	9	10	11	
Window (days)				±7	±7	±7	±7	±7	±7	±7	±7	±7	

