3.4.8. Missing Data

All available data will be included in the data analysis and presented in data listings and tabulations. Missing data will not be imputed for summaries of all safety endpoints and by-visit summaries of all the PD parameters.

For the primary analysis and secondary analyses, where a mixed model repeated measures (MMRM) model will be used, the missing data will be implicitly imputed assuming the missing assessments are missing at random (MAR).

To further assess the influence of missing data for the primary analysis, missing primary endpoint will be imputed using a controlled-based multiple imputation (MI) ([Rubin 1987](#), [Ouyang 2017](#)) method under an assumption of missing not at random (MNAR).

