3.5. Changes to Protocol Specified Analysis

There are no changes to the planned analysis.

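### The Month 12 cUHDRS ANCOVA drops subjects without a Month 12 score, leaves the interim TFC, TMS and SDMT scores unused, and has no missing-data plan, so dropout that differs by arm could bias it unchecked

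*SAP*

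**What the plan says.** **Model.** Protocol 9.3.3.2 specifies that "a MMRM analysis (repeat at visit) will be performed using all data collected up to 12 months". SAP 5.3 replaces this for the Month 12 change: "An ANCOVA model will be performed to compare each dose group with placebo group". The adjustment set is "baseline cUHDRS, disease stage, CAG, age, CAG by age interaction as covariates", so nothing measured after baseline enters except the Month 12 score. SAP Table 1 also names ANCOVA. SAP 3.5 nevertheless says "There are no changes to the planned analysis".

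**Data.** The cUHDRS formula in SAP 3.4.4 needs TFC, TMS, SDMT and Stroop word reading. The Protocol Table 4 note on the cognitive battery reads "Only SDMT is done at Visits 3, 4, 5, 6, and 7", so the full score is scheduled only on Day 1 and at Visit 8 or early termination. The motor and functional capacity parts are scheduled at Months 3, 6 and 9 alongside SDMT. SAP 5.4 plans only by-visit descriptive summaries of these components and an association analysis with biomarkers.

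**Missing data.** SAP 3.4.8 relies on implicit MAR handling where an MMRM is fitted, and plans control-based imputation for the primary endpoint. The cUHDRS ANCOVA falls under neither. Protocol 9.6 had left further detail to the SAP.

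**Windows.** SAP Table 2 opens the Month 12 window at Day 331 and closes it 30 days after the last dose. SAP 3.4.6 excludes anything later and applies the windows to early-termination visits too.

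**The concern.** Table 1 assigns the cUHDRS analysis to the ITT population, but the model can use only subjects with a score in the Month 12 window. Those who leave early may be those who declined faster or tolerated treatment poorly, and this may differ between active and placebo. The model adjusts for baseline characteristics but not for decline after baseline. The trial records that decline on three of the four components and then leaves it out of the comparison.

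cUHDRS is the only clinical scale among the secondary endpoints. As written, a reader of the results could not tell whether the estimate is sensitive to who was missing.

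**Working it through.** **1. Who is left out.** The Month 12 window opens on Day 331 and data end at last dose + 30 days. A usable score therefore needs a last dose on or after Day 331 - 30 = Day 301. A subject who stops before then has no usable Month 12 score even if assessed at Month 12, as Protocol 4.4 expects. An early-termination score before Day 331 maps to an earlier visit or to a gap in Table 2 (Days 121-150, 211-240 or 301-330). An early-termination score from Day 331 to last dose + 30 days does enter the ANCOVA.

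**2. Whether the protocol's MMRM solves it.** With no Stroop test at Visits 3-7, the full score has one scheduled post-baseline time point. A visit-repeated MMRM on cUHDRS would largely reduce to the ANCOVA.

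**3. The plan's own figures.** The documents give no SD, power or dropout rate for cUHDRS, so there is nothing to reproduce. The only sizing is for blood tHTT: 2 x (1.960 + 1.036)^2 / 0.85^2 = 24.85, close to the stated 24. It does not bear on this point.

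**4. Bias identity.** Let d be the share missing in an arm and g the completer mean minus the dropout mean, in SD of Month 12 change. The completer mean exceeds the full mean by d x g, so

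bias = d_active x g_active - d_placebo x g_placebo.

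- 10% missing in both arms, g = 0.5 in both: 0.05 - 0.05 = 0.
- 15% vs 5%, g = 0.5 in both: 0.075 - 0.025 = 0.05 SD.
- 20% vs 10%, g = 1 on active and 0 on placebo: 0.20 - 0 = 0.20 SD.

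**5. Size under an explicit mechanism (all inputs assumed).** Month 12 change = rho x Month 9 change + noise, with both changes at SD 1 and rho 0.6-0.8. The log-odds of dropout rise with Month 9 decline, with slope 0.5-1 in one arm and 0-0.5 in the other, and the same share is missing in each arm.

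| Missing | Complete-case bias (SD) |
|---|---|
| 10% | 0.03-0.07 |
| 20% | 0.05-0.14 |
| 30% | 0.07-0.20 |

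Equal slopes with no treatment effect give zero.

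A second simulation let subjects leave at Month 3, 6 or 9 according to their three-component composite:
- about 15% outcome-dependent dropout on active and 5% on placebo: +0.02 to +0.03 SD;
- about 20% per arm, outcome-dependent on active only: +0.05 to +0.06 SD;
- opposite directions in the two arms: about -0.06 SD;
- the same mechanism in both arms with a true effect of 0.4 SD: about -0.01 SD.

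The sign therefore depends on the mechanism.

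**6. Scale.** With both stages pooled there are 2 x 24 = 48 per active dose and 2 x 36 = 72 on placebo. The unadjusted full-data standard error is sqrt(1/48 + 1/72) = 0.186 SD. If only Parts A, B, D and E are filled, placebo is 144 / 3 = 48 and the standard error is sqrt(2/48) = 0.204 SD.

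**7. What imputation achieves.** When dropout depends on the observed interim scores, imputing from them brings the bias to about zero and reduces the empirical standard error by roughly 1-7%. When dropout instead depends on the Month 12 value itself (slope 1 in one arm, 10-30% missing), imputation from Month 9 still leaves 0.03-0.17 SD.

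**The case against.** The ANCOVA is a sensible response to the visit schedule. It is valid when missingness depends only on treatment, baseline cUHDRS, stage, CAG and age, all of which are in the model. Excluding data after last dose + 30 days is the stated intercurrent-event rule for every estimand in Table 1, not a peculiarity of this endpoint. The simulations favour imputation because dropout was made to depend on observed scores. cUHDRS is a non-key secondary endpoint in a Phase 2a trial, tested at nominal 0.05 without multiplicity control.

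Most of this stands. It rules out the stronger reading that the comparison is biased: the documents contain no dropout rate and no evidence that dropout is informative or differs by arm. A reader might also infer that every early-termination score is discarded; only those before Day 331 are. Nor would restoring the protocol's MMRM cure the problem.

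What does not stand is the absence of any stated assumption or check. The exclusion rule itself creates missing Month 12 scores. The SAP says how these are treated for its MMRM endpoints and is silent here.

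**Conclusion.** The point holds as a gap in the plan, not as a demonstrated bias. The cUHDRS comparison rests by default on subjects with a score in the Month 12 window, does not use relevant on-treatment data, and has no missing-data method or sensitivity analysis.

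Bias requires dropout that depends on post-baseline decline and differs between arms; an identical mechanism combined with a real effect gives only about 0.01 SD. The assumed range of about 0.02-0.20 SD runs from about a tenth of the standard error to slightly more than one. The upper end needs about 30% missing, a correlation of 0.8 and strongly outcome-dependent dropout in one arm only. The lower end is more typical of 10% missing. None of these inputs comes from the documents.

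Separately, the change from MMRM to ANCOVA contradicts the statement in SAP 3.5 and should be declared whatever is decided about imputation.

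**What to change.** Keep the Month 12 ANCOVA as the analysis model, and add to SAP 5.3 and 3.4.8:

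- **Imputation.** Multiply impute missing Month 12 cUHDRS under MAR within arm, from baseline cUHDRS, randomisation stratum, CAG, age, the available TFC, TMS and SDMT at Months 3, 6 and 9, and any early-termination cUHDRS, all restricted to last dose + 30 days. One three-component composite per visit keeps the model stable with about 48 per active arm. Use 100 imputations combined as in Appendix I.
- **Early-termination scores.** A cUHDRS before Day 331 exists only in subjects whose Month 12 score is missing, so completers cannot inform its coefficient. Its TFC, TMS and SDMT parts can enter the composite at a pre-specified visit, including when it falls in a window gap. The SAP should state any model used for the Stroop part.
- **Checks.** Report the complete-case ANCOVA alongside. Because MAR cannot be verified, add a control-based sensitivity analysis as for tHTT.
- **Declaration.** List the change from MMRM to ANCOVA in SAP 3.5, with the Stroop schedule as the reason.

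The cost is SAP wording and additional imputation runs on data already collected. The downside is reliance on MAR and on an imputation model. The precision gain is small, so the main benefit is protection against differential dropout and a visible check on it.
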